15.16 Potential Drug Interactions

The PK of ixazomib was similar with and without coadministration of clarithromycin, a strong CYP3A inhibitor, and therefore no dose adjustment is necessary when ixazomib is administered with CYP3A inhibitors. In the population PK analysis, coadministration of strong CYP1A2 inhibitors did not affect ixazomib clearance. Thus, no dose adjustment is required for patients receiving strong CYP1A2 inhibitors. In a clinical rifampin DDI study, ixazomib C_{max} and AUC0-last were reduced in the presence of rifampin by approximately 54% and 74%, respectively. As a result, the coadministration of strong CYP3A inducers with ixazomib is not recommended. Ixazomib is neither a time-dependent nor reversible inhibitor of CYPs 1A2, 2B6, 2C8, 2C9, 2C19, 2D6, or 3A4/5, therefore the potential for ixazomib to produce DDIs via CYP isozyme inhibition is low. Ixazomib did not induce CYP1A2, CYP2B6, and CYP3A4/5 activity. The potential for ixazomib to cause DDIs with substrates or inhibitors of P-gp, BCRP, MRP2, MATE-1, MATE2-K, OCT2, OAT1, OAT3, and OATPs is low.

Pharmacokinetic parameters for ixazomib coadministered with lenalidomide and dexamethasone (LenDex), are similar to those observed when ixazomib is administered as a single agent. This suggests that there is no readily apparent effect of coadministration of lenalidomide and dexamethasone on the clinical PK of ixazomib.

Ixazomib should not be taken if the patient has had a serious allergic reaction to boron or boron containing products.

15.17 **Known potential toxicities**

See the current version of the Investigator's Brochure for more complete information including potential risks, as well as recommendations for clinical monitoring and medical management of toxicity.

Very common ($\geq 10\%$): anemia, neutropenia, thrombocytopenia, constipation, diarrhea, nausea, vomiting, fatigue, decreased appetite, dizziness, peripheral neuropathy

Common ($\geq 1\%$ to $< 10\%$): Herpes zoster, peripheral sensory neuropathy, erythema, rash, erythematous rash, pruritic rash, macular rash, peripheral edema, upper respiratory tract infection, back pain, maculo-papular rash, popular rash

Uncommon ($\geq 0.1\%$ to $< 1\%$): generalized pruritis, generalized rash

Herpes zoster – antiviral prophylaxis should be considered in patients being treated with ixazomib to decrease the risk of herpes zoster reactivation.

Rare but serious risks – intestinal obstruction, pneumonia, life-threatening severe skin rash (Steven Johnson syndrome, TEN, DRESS syndrome), thrombotic thrombocytopenic purpura, tumor lysis syndrome, renal failure, posterior reversible encephalopathy syndrome, transverse myelitis, progressive multifocal leukoencephalopathy.

Overdose- There is no known specific antidote for ixazomib overdose. In the event of an overdose in blinded studies, study medication assignment should be unblinded immediately. The clinician should consider admitting the patient to the hospital for IV hydration, monitoring for adverse drug reaction, monitoring of vital signs, and appropriate supportive care. Gavage may be considered, but it should be kept in mind that ixazomib absorption is rapid. Ixazomib is not readily dialyzable.

15.18 **Drug procurement**

Investigational product will be supplied free of charge to trial participants by Millennium Pharmaceuticals, Inc.

Ixazomib Destruction: Investigational ixazomib (expired or end of study) should be destroyed on site according to the institution's standard operating procedure. Be sure to document removal and destruction on drug accountability logs.

15.2 Pomalidomide (Pomalyst®, CC-4047)

Please consult the most current Investigator's Brochure and package insert for complete drug information.

15.21 **Background:** Pomalidomide (CC-4047) is a novel drug in the class of immunomodulatory agents known as IMiDs compounds. Pomalidomide binds to its molecular target cereblon (CRBN), a protein that is part of an E3 ubiquitin ligase complex, which is responsible for the poly-ubiquitination of substrate proteins, targeting them for subcellular redistribution and destruction by the proteasome. The pharmacologic properties of pomalidomide are of potential therapeutic benefit in the treatment of various hematologic neoplasms (such as multiple myeloma and myeloproliferative neoplasm-associated myelofibrosis), non-neoplastic hematologic disorders (such as β -thalassemia and sickle cell disease) and non-hematologic disorders such as systemic sclerosis, as well as solid tumor neoplasms.

15.22 **Formulation:** Pomalidomide (CC-4047) capsules can be 0.5-mg gelatin capsules (size 4 reddish brown), 1-mg hard gelatin capsules (size 4 reddish brown), 2-mg (size 2 reddish-brown), 3-mg and 4-mg hard gelatin capsules (size 2 reddish-brown), and 5-mg hard gelatin capsules (size 1 reddish-brown), containing pomalidomide, mannitol, pregelatinized starch, and sodium stearyl fumarate.

Pomalidomide (CC-4047) capsules are supplied in high density polyethylene (HDPE) containers fitted with induction seals and child-resistant plastic closures or PVC/PCTFE blister with push-through foil.

15.23 **Preparation and storage:** Store drug at controlled room temperature, between 68-77 °F (20-25°C) or as indicated on the manufacturer's label. The expiration date is indicated on the label.

Only enough study drug for one cycle of therapy (one month) may be dispensed.

15.24 **Administration:** Pomalidomide is administered by mouth at approximately the same time each day with water. Pomalidomide should be taken without food, at least 2 hours before or 2 hours after a meal. Capsules should be swallowed whole, and should not be broken, chewed or opened. If a dose of pomalidomide is missed, it should be taken as soon as possible on the same day. If it is missed for the entire day, it should not be made up. Patients should be instructed never to give this medicinal product to another person and to return any unused capsules to the study doctor at the end of treatment. Patients who take more than the prescribed dose of pomalidomide should be instructed to seek emergency medical care if needed and contact study staff immediately.

15.25 **Pharmacokinetic information:**

a) Absorption – oral absorption has been moderately rapid with first dose- C_{max} occurring in 1.5 to 4 hrs. More than 70% of the pomalidomide dose is absorbed in humans. A high fat meal decreased the rate of absorption but had minimal effect on overall extent of absorption; therefore drug may be administered without regard to food intake.

b) Distribution – Apparent volume of distribution in healthy subjects ranged from 74-138 L across a dose range of 1 to 10 mg daily. Pomalidomide protein binding in human plasma is low to moderate (15.8% for R-enantiomer, 42.2% for S-enantiomer) and the binding is concentration independent in the concentration range of 30 and 1000 ng/mL. Drug distributes into semen.

c) Metabolism - Eight metabolites were detected in plasma, each at exposures <10% of the plasma pomalidomide. CYP-dependent metabolites accounted for approximately 43% of the excreted radioactivity, while non-CYP dependent hydrolytic metabolites accounted for 25%, and excretion of unchanged pomalidomide accounted for 10%.

d) Excretion – In healthy patients, 72.8% of the dose was recovered in urine and 15.5% was recovered in feces. Less than 3 % of the dose is excreted as unchanged pomalidomide in the urine. The geometric mean terminal elimination was approximately 7.5 hours.

15.26 **Potential Drug Interactions:** Pomalidomide is partially metabolized by CYP1A2 and CYP3A. Pomalidomide is also a substrate for P-glycoprotein (P-gp).

Coadministration of pomalidomide with the strong CYP3A4/5 and P-gp inhibitor ketoconazole, or the strong CYP3A4/5 inducer carbamazepine, had no clinically relevant effect on exposure to pomalidomide. Coadministration of the strong CYP1A2 inhibitor fluvoxamine with pomalidomide increased mean exposure to pomalidomide by 125% compared to pomalidomide alone. If strong inhibitors of CYP1A2 are coadministered with pomalidomide, the pomalidomide dose by should be reduced 50%.

Smoking: Administration of pomalidomide in smokers, with smoking tobacco known to induce the CYP1A2 isoform, had no clinically relevant effect on exposure to pomalidomide relative to that exposure to pomalidomide observed in non-smokers.

Dexamethasone: Co-administration of multiple doses of 4 mg pomalidomide with 20 mg to 40 mg dexamethasone (a weak inducer of CYP3A) to patients with multiple myeloma had no effect on the pharmacokinetics of pomalidomide compared with pomalidomide administered alone.

15.27 **Known potential toxicities:**

Very common known potential toxicities, $\geq 10\%$:

Anemia, leukopenia, neutropenia, thrombocytopenia, constipation, diarrhea, nausea, fatigue, peripheral edema, pyrexia, bronchitis, pneumonia, upper respiratory tract infection, decreased appetite, bone pain, muscle spasm, dizziness, peripheral neuropathy, blood creatinine increased, acute renal failure, cough, dyspnea, pruritis

Common known potential toxicities, $\geq 1\%$ - $<10\%$:

Febrile neutropenia, pancytopenia, vertigo, vomiting, gastrointestinal hemorrhage, hemorrhoidal hemorrhage, rectal hemorrhage, hematochezia, gingival bleeding, bronchopneumonia, herpes zoster, nasopharyngitis, neutropenic sepsis, respiratory tract infection, alanine aminotransferase increased, increased liver function test, aspartate aminotransferase increased, gamma-glutamyltransferase increased, neutrophil count decreased, platelet count decreased, white blood cell count decreased, hyperkalemia, hyponatremia, depressed level of consciousness, peripheral sensory neuropathy, paresthesia, gait disturbance, polyneuropathy, hypoesthesia, neuralgia, peripheral motor neuropathy, tremor, confusional state, renal failure, renal impairment, hypercreatininemia, urinary retention, pelvic pain, pulmonary embolism, pruritus generalized, rash, swelling face, face edema, deep vein thrombosis

Uncommon and rare known potential toxicities, <1%:

Melena, Mallory-Weiss syndrome, upper gastrointestinal hemorrhage, mucosal hemorrhage, hyperbilirubinemia, blood bilirubin increased, transaminases increased, blood alkaline phosphates increased, liver function test abnormal, basal cell carcinoma, dysesthesia, areflexia, motor dysfunction, sensory disturbance, burning sensation, muscle atrophy, blood urea increased, creatinine renal clearance decreased, oliguria, glomerular filtration rate decreased, renal tubular necrosis, acute prerenal failure, azotemia, pneumonitis, interstitial lung disease, pruritis generalized, angioedema, urticarial, eyelid edema

Frequency not defined:

Hepatitis, hepatitis B viral reactivation, tumor lysis syndrome, squamous cell carcinoma of skin, eye swelling, periorbital edema, lip swelling, swollen tongue, mouth edema, pharyngeal edema, Stevens-Johnson syndrome, toxic epidermal necrolysis, drug reaction with eosinophilia and systemic symptoms (DRESS)

All study participants must be registered into the mandatory POMALYST REMS™ program, and be willing and able to comply with the requirements of the POMALYST REMS™ program. Females of reproductive potential must adhere to the scheduled pregnancy testing. Females of childbearing potential should not handle or administer pomalidomide unless they are wearing gloves.

- 15.28 **Drug procurement:** Pomalidomide (POMALYST®) will be provided to research subjects for the duration of their participation in this trial at no charge to them or their insurance providers. Pomalidomide will be provided in accordance with Celgene Corporation's POMALYST REMS™ program. Per the standard POMALYST REMS™ program requirements, all physicians who prescribe pomalidomide for research subjects enrolled into this trial, and all research subjects enrolled into this trial, must be registered in and must comply with all requirements of the POMALYST REMS™ program.

Drug will be shipped on a per patient basis by the contract pharmacy to the clinic site for IND studies. Only enough pomalidomide for one cycle of therapy will be supplied to the patient each cycle.

15.3 Dexamethasone for Oral Administration (DXM)

- 15.31 **Background:** Dexamethasone is an adrenal corticosteroid compound. Dexamethasone decreases inflammation by suppression of neutrophil migration, decreased production of inflammatory mediators, and reversal of increased capillary permeability; suppresses normal immune response. Dexamethasone's mechanism of antiemetic activity is unknown.
- 15.32 **Formulation:** Commercially available for oral administration as:
Tablets [scored]: 0.5 mg, 0.75 mg, 1 mg, 1.5 mg, 2 mg, 4 mg, and 6 mg
Solution, oral: 0.5 mg/mL (500 mL)
Solution, oral concentrate: Dexamethasone Intensol: 1 mg/mL (30 mL)
- 15.33 **Preparation, storage, and stability:** Refer to package insert for complete preparation and dispensing instructions. Store oral tablets at room temperature between 20°C to 25°C (60°F to 77°F). Protect from moisture. Dispense in a well-closed, light-resistant container as defined in the USP/NF. Store oral liquid at room temperature, do not freeze. Do not use

if solution contains a precipitate. Refer to commercial package for drug expiration date.

15.34 **Administration:** Refer to the treatment section for specific administration instructions. May be taken with meals to decrease GI upset.

15.35 **Pharmacokinetic information:**

Onset of action: Prompt

Duration of metabolic effect: 72 hours

Metabolism: Hepatic

Half-life elimination: Normal renal function: 1.8-3.5 hours; **Biological half-life:** 36-54 hours

Time to peak, serum: Oral: 1-2 hours

Excretion: Urine and feces

15.36 Potential Drug Interactions:

Cytochrome P450 Effect: Substrate of CYP3A4 (major); **Induces** CYP2A6 (weak), 2B6 (weak), 2C8 (weak), 2C9 (weak), 3A4 (strong)
Increased Effect/Toxicity: Aprepitant, azole antifungals, calcium channel blockers, cyclosporine, estrogens, and macrolides may increase the serum levels of corticosteroids. Corticosteroids may increase the hypokalemic effects of amphotericin B or potassium-wasting diuretics (loop or thiazide); monitor. Refer to the package insert for a listing of other drugs.
Decreased Effect: Antacids and bile acid sequestrants may reduce the absorption of corticosteroids; may reduce the absorption of corticosteroids; separate administration by 2 hours. Aminoglutethimide, barbiturates, and CYP3A4 inducers may reduce the serum levels/effects of dexamethasone and dexamethasone may decrease the levels/effects of other CYP3A4 substrates. Serum concentrations of isoniazid may be decreased by corticosteroids. Corticosteroids may lead to a reduction in warfarin effect. Corticosteroids may suppress the response to vaccinations.

Ethanol/Nutrition/Herb Interactions:

Ethanol: Avoid ethanol (may enhance gastric mucosal irritation).
Food: Dexamethasone interferes with calcium absorption. Limit caffeine.
Herb/Nutraceutical: Avoid cat's claw (*Uncaria tomentosa*), echinacea (have immunostimulant properties)

15.37 Known potential adverse events: Consult the package insert for the most current and complete information.**Common known potential toxicities,** frequency not defined:

Fluid and electrolyte disturbances, congestive heart failure in susceptible persons, hypertension, euphoria, personality changes, insomnia, exacerbation of infection, exacerbation or symptoms of diabetes, psychosis, muscle weakness, osteoporosis, vertebral compression fractures, pancreatitis, esophagitis, peptic ulcer, dermatologic disturbances, convulsions, vertigo and headache, endocrine abnormalities, ophthalmic changes, and metabolic changes. Some patients have experienced itching and other allergic, anaphylactic or hypersensitivity reactions. Withdrawal from prolonged therapy may result in symptoms including fever, myalgia and arthralgia.

15.38 Drug procurement: Commercial supplies. Pharmacies or clinics shall obtain supplies from normal commercial supply chain or wholesaler.

16.0 Statistical Considerations and Methodology

16.1 Overview

This is a phase II study of a novel regimen of ixazomib with pomalidomide and dexamethasone for treatment of multiple myeloma with extramedullary disease and plasma cell leukemia. The study is designed to assess the confirmed response rate using a single stage phase II study design with an interim analysis. Accrual will be halted after 6 patients to assess safety (see Section 16.4). We do not plan to halt accrual during the interim analysis (see Section 16.214).

16.11 Primary Endpoint: The primary endpoint of this trial is the rate of confirmed response. A confirmed response is defined as a patient who has achieved an sCR, CR, VGPR, or PR on two consecutive evaluations. All patients meeting the eligibility criteria, who have signed a consent form and have begun treatment, will be evaluable for response, unless they are determined to be a major violation.

16.2 Statistical Design

16.21 Decision Rule: The largest success proportion where the proposed treatment regimen would be considered ineffective in this population is 25%, and the smallest success proportion that would warrant subsequent studies with the proposed regimen in this patient population is 50%. The following one-stage design with an interim analysis is based on a two-stage Simon optimum design and requires 27 evaluable patients to test the null hypothesis that the true success proportion in this patient population is at most 25%.

16.211 Interim Analysis: Enter 10 evaluable patients into the study. If 2 or fewer successes are observed in the first 10 evaluable patients, we will consider this regimen ineffective in this patient population and terminate the study. Otherwise, if the number of successes is at least 3, we will continue accrual.

16.212 Final Decision Rule: Enter an additional 17 evaluable patients into the study. If 9 or fewer successes are observed in the first 27 evaluable patients, we will consider this regimen ineffective in this patient population and terminate this study. Otherwise, if the number of successes is at least 10, this will be considered evidence of promising activity and the treatment may be recommended for further testing in subsequent studies in this population.

16.213 Over Accrual: If more than the target number of patients are accrued, the additional patients will not be used to evaluate the stopping rule or used in any decision making process. Analyses involving over accrued patients are discussed in Section 16.313.

16.214 NOTE: We will not suspend accrual at the interim analysis to allow the first 10 patients to become evaluable, unless undue toxicity is observed. Given the limited overall sample size and the inclusion of an adverse events stopping rule, we feel it is ethical to not halt accrual for the interim analysis. However, if accrual is extremely rapid, we may temporarily suspend accrual in order to obtain safety data on these patients before re-opening accrual to further patients.

- 16.22 **Sample Size:** The one stage study design with an interim analysis to be used is fully described below. A minimum of 10 and a maximum of 27 evaluable patients will be accrued onto this phase II study unless undue toxicity is encountered. We anticipate accruing additional 3 patients to account for ineligibility, cancellation, major treatment violation, or other reasons for a total of 30 patients overall.
- 16.23 **Accrual Rate and Study Duration:** The anticipated accrual rate is 1-2 evaluable multiple myeloma patients per month. At this rate, it will likely take about 18-24 months to enroll, treat, and evaluate all patients. The maximum total study duration is expected to be approximately 2.5 years, or until the last patient accrued has been observed for at least 6 months.
- 16.24 **Power and Significance Level:** Assuming that the number of successes is binomially distributed, the significance level is .10, i.e. there is a 10% chance of finding the drug to be effective when it truly is not. The probability of declaring that this regimen warrants further study (i.e. statistical power) and the probability of stopping at the interim analysis under various success proportions can be tabulated as a function of the true success proportion as shown in the following table.

If the true success proportion is...	0.25	0.30	0.35	0.40	0.45	0.50
Then the probability of declaring that the regimen warrants further study is...	0.10	0.24	0.44	0.64	0.80	0.90
And the probability of stopping at the interim analysis is...	0.53	0.38	0.26	0.17	0.10	0.05

- 16.25 **Other considerations:** Adverse events, quality/duration of response, and patterns of treatment failure observed in this study, as well as scientific discoveries or changes in standard care will be taken into account in any decision to terminate the study.

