8.11 Instruction for initiation of a new cycle of therapy

A new cycle of treatment may begin on the scheduled Day 1 of a new cycle if:

- The ANC is $\geq 1000/\mu\text{L}$
- The platelet count is $\geq 50,000/\mu\text{L}$
- Any other non-hematologic treatment -related adverse event that may have occurred has resolved to \leq Grade 1 or baseline severity.

If these conditions are not met on Day 1 of a new cycle, the subject will be evaluated weekly and a new cycle of therapy will be held until the toxicity has resolved as described above.

If any drug dosing was halted during the previous cycle and was restarted with a one-level dose reduction without requiring an interruption for the remainder of the cycle, then that reduced dose level will be initiated on Day 1 of the new cycle.

If any drug dosing was omitted for the remainder of the previous cycle or if the new cycle is held due to known hematologic toxicity newly encountered on the scheduled Day 1, then the new cycle will be started with a one-level dose reduction. If a new cycle of therapy cannot be restarted within 4 weeks of the scheduled Day 1 due to non-resolution of drug related toxicities, the patient will be removed from protocol therapy and will go to event monitoring.

→ → Use the NCI Common Terminology Criteria for Adverse Events (CTCAE) version 4.0* unless otherwise specified ← ←

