16.3 Analysis Plan

The analysis for this trial will commence at planned time points (see 16.2) and at the time the patients have become evaluable for the primary endpoint. The Statistician and Study Chair will make the decision, in accord with CCS Standard Operating Procedures, availability of data for secondary endpoints (e.g., laboratory correlates), and the level of data maturity. It is anticipated that the earliest date in which the results will be made available via manuscript, abstract, or presentation format is when last patient has been followed for at least 6 months.

16.31 Primary Outcome Analyses:

16.311 **Definition:** The primary endpoint of this trial is the proportion of the confirmed response rate. A success is defined as an sCR, CR, VGPR, or PR noted as the objective status on two consecutive evaluations. All patients meeting the eligibility criteria who have signed a consent form and have begun treatment will be evaluable for response, unless they are determined to be a major violation.

16.312 **Estimation:** The proportion of successes will be estimated by the number of successes divided by the total number of evaluable patients. Ninety-

five percent confidence intervals for the true success proportion will be calculated according to the approach of Duffy and Santner.

- 16.313 Over Accrual: If more than the target number of patients are accrued, the additional patients will not be used to evaluate the stopping rule or used in any decision making processes; however, they will be included in final point estimates and confidence intervals.

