16.4 Early Safety Analysis

An early safety analysis will be performed after the first 6 patients have been accrued to the study and observed for one cycle. Accrual will be temporarily halted while these patients are evaluated. If 2 or more of the first 6 patients experience a DLT as defined below, then accrual to the study will continue to be temporarily halted while the study team determines if changes to the dosing schedule are warranted.

Toxicity will be measured per NCI-CTCAE version 4. DLT is defined as an adverse event occurring during the first cycle of treatment that is possibly, probably, or definitely related to study treatment and that meets one of the following:

- Grade 3 diarrhea, nausea, and fatigue lasting > 3 days despite optimal supportive medications
- Any other \geq Grade 3 non-hematological toxicity with the exceptions of electrolyte abnormalities that are reversible and asymptomatic
- Febrile neutropenia
- Grade 3 thrombocytopenia with clinically significant bleeding
- Any \geq Grade 4 neutrophil count decreased or platelet count decreased that persists >7 days

16.5 Data & Safety Monitoring:

16.51 The principal investigator(s) and the study statistician will review the study at least twice a year to identify accrual, adverse event, and any endpoint problems that might be developing. The Mayo Clinic Cancer Center (MCCC) Data Safety Monitoring Board (DSMB) is responsible for reviewing accrual and safety data for this trial at least twice a year, based on reports provided by the MCCC Statistical Office.

16.52 Adverse Event Stopping Rules: The stopping rules specified below are based on the knowledge available at study development. We note that the Adverse Event Stopping Rule may be adjusted in the event of either (1) the study re-opening to accrual or (2) at any time during the conduct of the trial and in consideration of newly acquired information regarding the adverse event profile of the treatment(s) under investigation. The study team may choose to suspend accrual because of unexpected adverse event profiles that have not crossed the specified rule below.

Accrual will be temporarily suspended to this study if at any time we observe events considered at least possibly related to study treatment (i.e. an adverse event with attribute specified as “possible,” “probable,” or “definite”) that satisfy one of the following:

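### Does the futility look at 10 patients need a stated minimum follow-up, given that a plasmacytoma response first imaged at Cycle 4 may wait until Cycle 7 for its confirming scan?

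*Combined protocol and SAP*

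**What the plan says.** **The rule.** Section 16.211: "If 2 or fewer successes are observed in the first 10 evaluable patients, we will consider this regimen ineffective". With three or more successes accrual goes on, and Section 16.212 calls the regimen promising at 10 or more of 27.

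**Who counts.** Section 16.11: "All patients meeting the eligibility criteria, who have signed a consent form and have begun treatment, will be evaluable for response", with major violations excepted. No follow-up time is part of this.

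**What counts.** Section 16.311: "A success is defined as an sCR, CR, VGPR, or PR noted as the objective status on two consecutive evaluations". Section 11.1 keeps unconfirmed categories as an internal working status that guides decisions and the ordering of tests. Footnote a of Table 11.5 asks for two consecutive assessments before any new therapy and sets no interval between them.

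**When to look.** Section 16.214: "We will not suspend accrual at the interim analysis to allow the first 10 patients to become evaluable". Section 16.3 starts analysis when patients are evaluable for the primary endpoint. It leaves the decision to the Statistician and Study Chair, under their operating procedures and with regard to "the level of data maturity". Section 16.25 adds that "Adverse events, quality/duration of response, and patterns of treatment failure observed in this study" will bear on any decision to terminate. The 6-month minimum in 16.23, 16.3 and 16.6 concerns the last patient and final reporting.

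**Assessment schedule.** Footnote 8 of the Section 4.0 test schedule puts imaging of extramedullary lesions at the end of Cycle 1 and every three cycles after that, or sooner if clinically indicated. Footnote 9 puts circulating plasma cells after Cycle 1 and every two cycles after that. Palpable lesions are measured every cycle.

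**The concern.** Read literally, the ten patients are evaluable as soon as the tenth has started treatment, so the count could be taken before a confirmed response is possible. A plasmacytoma response first imaged at the end of Cycle 4 has its next scheduled scan at the end of Cycle 7. That is later than six months and later still after a cycle hold; Section 8.11 removes a patient only "If a new cycle of therapy cannot be restarted within 4 weeks of the scheduled Day 1". No section says whether such a response needs a second lesion measurement, or whether the status at the next per-cycle visit is enough.

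A patient with a response awaiting confirmation is not yet a success. If the look did not wait for such patients, a working regimen could be stopped for futility, and the stopping probability and power tabulated in Section 16.24 would not hold. The error would run one way only: more false stops and less power, with no inflation of type I error.

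**Working it through.** **1. Reproduce the plan's figures.** Inputs from 16.21 to 16.24: null 0.25, alternative 0.50, stop at 2 or fewer of 10, promising at 10 or more of 27.

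- Stop at p = 0.50: P(Bin(10, 0.5) ≤ 2) = (1 + 10 + 45)/1024 = 0.0547 (table: 0.05).
- Promising: sum over x = 3 to 10 of P(Bin(10, p) = x) × P(Bin(17, p) ≥ 10 − x). This is 0.9036 at p = 0.50 (table: 0.90) and 0.0994 at p = 0.25 (table: 0.10).

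The table is right when all ten outcomes are final.

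**2. Scan dates.** With 28-day cycles, scans fall on treatment days 28, 112 and 196. The Cycle 7 scan is at day 196 − 7 = 189 at the early edge of the visit window. At the latest it is day 196 + 7 + 14 = 217 from registration, because treatment may start up to 14 days after registration. Six months is about 183 days.

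**3. What an early look would do.** The documents give no data on response timing, so these are assumptions:

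- true confirmed response rate 50%;
- all ten patients have imaged-only disease, with no early scan;
- a share f of responders, 0.25 to 0.75, is first seen at Cycle 4 and the rest at Cycle 1;
- treatment starts 0 or 14 days after registration (the lag);
- accrual is 1 or 2 per month (16.23), with the halt in 16.4 included: "An early safety analysis will be performed after the first 6 patients have been accrued to the study and observed for one cycle".

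At the look, a patient counts as a success with probability 0.5(1 − f) once followed for 112 days plus the lag. A further 0.5f is added once followed for 196 days plus the lag. The chance that ten such patients give 2 or fewer successes is:

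| Look after 10th entry | 1 per month | 2 per month |
|---|---|---|
| 3 months | 0.136–0.287 | 0.240–0.553 |
| 4 months | 0.085–0.187 | 0.098–0.262 |
| 5 months | 0.073–0.118 | 0.085–0.239 |
| 6 months | 0.063–0.081 | 0.063–0.118 |
| 7.2 months | 0.055 | 0.055 |

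Worked cell: at 6 months and 1 per month, nine patients are final and the tenth counts with probability q = 0.5(1 − f). For nine patients, P(≤ 1) = 10/512 = 0.0195 and P(≤ 2) = 46/512 = 0.0898. With f = 0.75, q = 0.125, so the stop probability is 0.125 × 0.0195 + 0.875 × 0.0898 = 0.081. With f = 0.25, q = 0.375, which gives 0.063.

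Overall power is 0.694–0.833 (1 per month) or 0.439–0.738 (2 per month) for the 3-month look, and 0.849–0.896 for the 6-month look.

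**4. Milder cases.** If half of the ten are imaged-only, the false stop is 0.073–0.287 at 3 months and 0.055–0.081 at 6 months. If the next per-cycle evaluation can confirm without a second scan, it is 0.073–0.239 at 3 months and 0.055 at 6 months.

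**5. Cost of a fixed Cycle 7 rule.** 217 days is 7.13 months. At 1 to 2 per month that is about 7 to 14 further patients, so 17 to 24 of 27 could be enrolled before a futility stop.

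**The case for a change.** The best argument for a change is that ending a trial should not rest on unstated discretion. The definition of evaluable supplies no waiting time, 16.3 names maturity without a threshold, and 16.214 speaks of patients becoming evaluable although by 16.11 they already are. Wording costs no scans. A futility stop could wait while a trial with three confirmed successes simply goes on. Even the milder cases raise the false-stop probability at 3 months above 0.055.

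What stands is that 16.211 names no follow-up time and does not say whether the look waits for pending responses. The rest is weaker.

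- **The status of an unconfirmed response is settled.** Under 16.11 and 16.311 it is not a success. The only open matter is whether to wait for it.
- **The text leans toward waiting.** Talk of letting the first ten become evaluable makes no sense if starting treatment were enough, and 16.3 ties analysis to the primary endpoint. Accrual continues, so nothing presses for an early count.
- **The large figures need an unlikely look.** At 3 months, about 91 days, the tenth patient has not reached the day-112 scan, so in this model that patient cannot be a confirmed success. A statistician would not call such data mature.
- **The Cycle 7 wait is conditional.** Earlier scans are allowed, an unconfirmed response may prompt one, and M-protein, free light chains, palpable or skin lesions, or circulating plasma cells may confirm sooner.
- **A firm rule has its own price.** Counting every patient without confirmation by Cycle 7 as a failure adds a time limit that 16.311 lacks. If 10% of responders first respond at Cycle 7 or later, the countable rate is 0.5 × 0.9 = 0.45. Applied to the final analysis, the plan's own table then gives power 0.80 instead of 0.90. Counting treatment discontinuation as failure would conflict with footnote a of Table 11.5, which lets confirmation come at any time before new therapy.

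**Conclusion.** No change is needed. This is a missing detail that the people named in 16.3 can be expected to fill sensibly: they would not declare futility while a pending response among the first ten could still bring the count to three. With a look at 6 months or later, the false-stop probability at a true 50% is at most about 0.12 even if all ten have imaged-only disease. It returns to the planned 0.055 once all ten have passed Cycle 7. The larger values, up to 0.55, depend on a 3-month look that no section prescribes and on assumed response timing. Type I error is not inflated. The 6-month text in 16.23, 16.3 and 16.6 is a floor and already allows a longer wait. A fixed Cycle 7 rule would trade a modest gain in certainty for a futility look that comes when 17 to 24 of 27 patients may be enrolled, so leaving the timing to judgement is a fair choice.
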